## Study Protocol

The purpose of this study is to expand upon a previous study of maternal addiction, by conducting a randomized, double-blinded, placebo controlled, crossover study of intranasal oxytocin (OT) on maternal brain responses. 150 mothers from the University of Iowa and the Yale Child Study Center will be enrolled (75 with a history of drug addiction and 75 matched control mothers), along with their 2 to 12-month-old infants, to participate in four study visits over a two-month period.

**Oxytocin administration and neuroimaging procedures.** In this double-blinded placebo-controlled crossover challenge of intranasal OT, maternal brain responses to infant face cues and cries were assessed between participants on receiving either the active (OT) or the inactive (placebo) nasal spray prior to one of two fMRI scanning sessions. Participants, investigators and data analysts were blinded to the identity of the OT and placebo sprays. Infant face images were presented during each scanning session. Specifically, infant face images were presented from each of the four following face conditions: the mother's own infant's face (happy and sad) and an unknown infant's face (happy and sad).

Current smokers were allowed the opportunity to smoke 60 min prior to the scanning session, to avoid any confounding effects of acute nicotine intoxication or withdrawal. All participants will take a urinary pregnancy test prior to the start of the visit. If a mother tested positive, she was excluded from the study due to theoretical concerns about effects of OT and MRI exposure on the pregnancy. The urine sample was used to screen for recent drug use, using the RediCup 5 drug test (for amphetamines, cocaine, marijuana, opioids and benzodiazepines).

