## Statistical Analysis Plan

A mixed effects model with random intercepts was run in R (version 4.2.2) using the lme4 package. Given the repeated measures design and the fact that there were incomplete data (i.e., not all subjects were in the OT and placebo condition), the mixed effects model provides a way of examining the effect of condition, controlling for the fact within-subjects nature of the study. For Hypothesis 1, which focuses on the effect of OT vs. placebo, on the condition variable was included in the model. For Hypothesis 2, group (addiction and controls) as well as condition was included. The interaction between group and condition was initially explored. Since there were no significant interaction effects, they were not included in subsequent analyses. P-values from the mixed-effects models were obtained using the Kenward-Roger approximation. Estimated marginal means and their standard errors were obtained from the model results using the R package “modelbased” (<https://cran.r-project.org/web/packages/modelbased/index.html>).

Anatomically-defined regions of interest (ROIs) based on the Harvard-Oxford Atlas were used to extract fMRI BOLD data representing the contrast of Happy own faces vs. Happy unknown faces or Sad own faces vs. Sad unknown faces. The contrasts represent data across all four task runs.

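### An unlisted set of brain regions is tested on two unranked face contrasts with no stated alpha or multiplicity adjustment

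*Combined protocol and SAP*

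**What the plan says.** The SAP section is short, and everything on this point is in it.

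- **Regions.** "Anatomically-defined regions of interest (ROIs) based on the Harvard-Oxford Atlas were used to extract fMRI BOLD data". The plural implies at least two regions. None is named and no number is given.
- **Contrasts.** The extracted data represent the "contrast of Happy own faces vs. Happy unknown faces or Sad own faces vs. Sad unknown faces". Neither contrast is called primary, and no testing order is set.
- **Hypothesis 1.** "For Hypothesis 1, which focuses on the effect of OT vs. placebo, on the condition variable was included in the model". The tested term is condition (oxytocin versus placebo).
- **Hypothesis 2.** "For Hypothesis 2, group (addiction and controls) as well as condition was included". This lists model terms; it does not say which coefficient carries the hypothesis.
- **Interaction.** "The interaction between group and condition was initially explored", and then "Since there were no significant interaction effects, they were not included in subsequent analyses". No significance threshold is given.
- **P-values.** "P-values from the mixed-effects models were obtained using the Kenward-Roger approximation". No alpha, sidedness, family of tests, adjustment or rule for combining regions goes with this.

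On scope, the Study Protocol says that "maternal brain responses to infant face cues and cries were assessed", and its fMRI parameters list OC and UC trials beside the four face types. The SAP mentions only faces.

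**The concern.** The plan tests numbered hypotheses with p-values in several regions and on two contrasts, so each hypothesis has several chances to produce a nominally significant result. Kenward-Roger improves the standard error and degrees of freedom of a single test; it does nothing about error across tests. With no list of regions, no alpha and no adjustment, a reader cannot count the tests behind a hypothesis. A report that one region responded to oxytocin on one contrast could then be one success in two tests or one in twenty, and the plan gives no way to tell which.

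**Working it through.** **Is there a figure to reproduce?** No. The plan states no alpha, number of tests, power or effect size. What follows is an illustration under stated assumptions.

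**Inputs**
- Contrasts per region: 2 (SAP).
- Coefficients per hypothesis: 1 (condition for Hypothesis 1; one coefficient, not named, for Hypothesis 2).
- Regions: not given. Assumed 2, 5 or 10.
- Alpha per test: not given. Assumed 0.05, two-sided.
- Correlation between test statistics: not given. Taken from 0 to 0.99.

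**Step 1: number of tests per hypothesis.** m = 2 × regions, so 2, 5 or 10 regions give m = 4, 10 or 20.

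**Step 2: independent tests.** Chance of at least one false positive = 1 − 0.95^m.
- m = 4: 1 − 0.8145 = 18.5%
- m = 10: 1 − 0.5987 = 40.1%
- m = 20: 1 − 0.3585 = 64.2%

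**Step 3: correlated tests.** Regions and contrasts come from the same mothers, so correlation is likely. With equally correlated standard normal statistics at correlation ρ, the chance is

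1 − ∫ φ(u) [Φ((1.96 − √ρ·u)/√(1−ρ)) − Φ((−1.96 − √ρ·u)/√(1−ρ))]^m du,

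integrated numerically over the common factor u.

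| Regions (tests) | ρ = 0 | 0.5 | 0.8 | 0.95 | 0.99 |
|---|---|---|---|---|---|
| 2 (4) | 18.5% | 15.6% | 11.4% | 8.0% | 6.3% |
| 5 (10) | 40.1% | 28.7% | 17.3% | 10.0% | 7.0% |
| 10 (20) | 64.2% | 41.9% | 22.4% | 11.6% | 7.5% |

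Every cell exceeds 5%. At ρ = 1 the tests would be one test and the chance would be exactly 5%.

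**Step 4: with Holm.** When all null hypotheses are true, Holm makes at least one error only if the smallest p-value is at or below 0.05/m: 0.0125, 0.005 or 0.0025 for m = 4, 10 or 20. Putting that threshold into the same formulas gives a family-wise error of 4.9% for each m at ρ = 0, and 2.2%, 1.2% and 0.8% at ρ = 0.95. Holm therefore keeps error at or below 5%, but it is conservative when regions move together.

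**Step 5: what adjustment costs.** Take a comparison of the planned 75 and 75 mothers that has 80% power unadjusted. The standardised difference is (1.960 + 0.842) × √(2/75) = 0.457. At 0.05/10 the critical value is 2.807 and power is Φ(2.802 − 2.807) = 50%. At 0.05/20 the critical value is 3.023 and power is Φ(2.802 − 3.023) = 41%. These are Bonferroni figures for a single region. Holm does no worse.

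**The case against.** The strongest objection is that the sizes come wholly from assumptions. Across the table they run from 6.3% to 64.2%, driven by an assumed region count, correlation and alpha. That stands: no cell is a property of this plan or a floor set by it. What the table supports is the direction: above 5% whenever two or more imperfectly correlated tests are each run at 0.05.

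A second objection is that Holm is only one choice and can be costly. This also stands, as Steps 4 and 5 show, and it is why a method that uses the correlation belongs among the options.

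Three stronger readings are tempting, and the documents do not support them.

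- **That the regions or contrasts were picked after the results were seen.** The SAP is in the past tense and reports an interaction result, so this text was written after at least some analysis. That does not show when the regions and contrasts were chosen. Earlier choice is neither shown nor excluded.
- **That Hypothesis 2 has no identifiable test, or that condition is counted twice.** Hypothesis 1 is tied to oxytocin versus placebo, and group is the only term Hypothesis 2 adds once the interaction is dropped. Group is the natural reading. It remains an inference, because a group difference in average response and a group difference in the response to oxytocin are different questions. One sentence settles it.
- **That a cry analysis was suppressed.** The SAP names only face contrasts, and the protocol's list of conditions and its post-scan ratings concern faces, so a face-only scope is quite possible. OC and UC are never spelled out. The gap is an unstated scope; it is no evidence of selective reporting.

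**Conclusion.** The concern holds in this form: the SAP applies per-test p-values to an unlisted, uncounted set of regions and two unranked face contrasts, with no alpha and no adjustment. If region-by-contrast tests are run separately at 0.05, the false-positive chance per hypothesis exceeds 5% unless the tests are perfectly correlated. How far it exceeds 5% cannot be fixed from the plan. With 5 regions, for example, it is 40.1% under independence and 10.0% at correlation 0.95.

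The sponsor should correct this, because a cheap and better method exists. The Hypothesis 2 coefficient and the place of cries are clarifications that would not justify a finding by themselves.

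**What to change.** 1. **List and date the tests.** Name every region and contrast analysed, state alpha, and say whether each was chosen before or after the data were seen. The authors should report the timing as it was; they should not be asked to declare the choices post hoc.
2. **Name the coefficient.** Condition for Hypothesis 1. For Hypothesis 2, group or the group-by-condition interaction, whichever was intended. Call the interaction exploratory only if it is not the Hypothesis 2 test.
3. **Adjust within each hypothesis.** Apply Holm, or a correlation-aware alternative such as a permutation max-statistic, across all regions × contrasts tested under that hypothesis. Report adjusted beside raw p-values, and say that this controls error per hypothesis and not across both.
4. **Minor: state whether cries are in scope.** If a cry contrast is tested under the same hypothesis, put it in that hypothesis's family, or say that error is controlled per stimulus type only. Two separate 5% families under one hypothesis could reach 1 − 0.95² = 9.75% if independent.

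**Cost.** A written list, a sentence per hypothesis, a scope sentence and, for Holm, one adjustment call per family; no new data. Adjusted p-values will be larger and some nominal findings may be lost. The power loss is real, since at correlation 0.95 Holm runs at about 1 to 2% family-wise error for 4 to 20 tests. A permutation max-statistic would recover some of that power. It takes more work, because the permutation scheme must respect the crossover and the mothers who lack one of the two conditions.
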